### **Sample Size and Population**

The target population is 44 participants, 22 in each group. Randomization will be stratified by type of cancer (colon, rectal/other better prognosis GI cancers, poorer prognosis cancers) and cancer stage (localized stages II/III or metastatic stage IV) to minimize differences between groups (6 strata total). We will add cancers of the small intestine, anus and appendix to our existing rectal cancer strata since the survival rates are similar. The cancer types with poorer prognoses will be put into the new strata (with <50% 5-year survival rate; cancers of the esophagus, stomach, pancreas, gallbladder, liver).

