## 2. BACKGROUND AND RATIONALE

### 2.1 Background on Condition, Disease, or Other Primary Study Focus

**Burden of fatigue and depressive symptoms in gastrointestinal cancers is high.** Gastrointestinal (GI) cancers are among the most prevalent cancers for both men and women, and the number of GI survivors continues to increase. Fatigue, “a subjective state of overwhelming and sustained exhaustion and decreased capacity for physical and mental work that is not relieved by rest,” is reported by a majority (>50%) of patients with GI cancers, co-occurs with other common symptoms such as depression (>30% in patients receiving chemotherapy), and is associated with a decline in post-treatment quality of life. There is overlap in some methods for assessing fatigue and depressive symptoms; however, these symptoms remain moderately correlated even when commonalities are removed. There is also considerable evidence showing that fatigue and depression are distinctly associated with other variables such as quality of life. Further, although chemotherapy is efficacious for increasing survival, it leads to increases in fatigue and depressive symptoms such that symptoms peak approximately 3-5 days following treatment and then improve, however fatigue and depressive symptoms do not return to pretreatment levels in a substantial subset of patients (20-80%). Fatigue and depressive symptoms experienced during treatment are associated with subsequent symptoms. Thus, it is important to address elevations of fatigue and commonly co-occurring depressive symptoms during chemotherapy to improve quality of life in patients with GI cancers.

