Based on prior longitudinal work with patients from similar populations, we are anticipating approximately 15% dropout (from N=44). From previous research in a mixed sample of cancer patients, the variability in the values of the PROMIS 7-item fatigue measure used in this study is a standardized standard deviation of 8 points (Mean t-score=53.6). Effect sizes in preliminary studies of yoga for fatigue as compared to an active control in patients with cancer range from 0.33 to 1.50. This variability may be explained in part by study quality and patients' initial levels of fatigue. We expect that daily assessments of fatigue and depressive symptoms will detect these symptoms at their nadir and thus may be more sensitive to such phenomena than recalled measures. Therefore, it is important to obtain a good estimate of the variance of fatigue in this group to use in future studies. Power calculations for a subsequent larger study will be based on clinically meaningful differences between the groups on the primary outcome using estimates of SD. With a sample size of 44, the probability is 0.80 (80% confidence) that the estimate of the standard deviation (SD) will be no more than 10% of the true population SD below the true population SD; if the SD varies by group, there is 80% confidence that the estimate of the SD is no more than 14% below the true SD.

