### **Treatment Assignment Procedures**

Eligible, consented, and enrolled participants will be randomized to YST or AC. To control for type and stage of cancer, randomization will occur within both type (colon, rectal/other better prognosis GI cancers, poorer prognosis cancers) and stage (localized stages II/III or metastatic stage IV). There is not a sample size goal within strata. Given this relatively small preliminary study, it was deemed more efficient and enabled tighter control over known influences on outcome to stratify rather than to use statistical control via covariate analysis. The other alternative would have been to use only a single type/stage of cancer, which was not feasible due to too few cases at VICC and CCC-WFU. The population of the cancer patients with the types/stages selected was sufficient at VICC and CCC-WFU to enable randomization within thus increasing generalizability potential.

Randomization (1:1) lists within each strata will be generated via a permuted block program developed and executed by the study biostatistician with blocks of random sizes between 2 and 6. The randomization lists will be held by a staff member (not involved with data collection) who will allocate each participant to study group. STM who are collecting data will not be informed of group assignment.

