**Specific Aim 2.** A critical element of this proposal is the inclusion of daily (vs. standard recalled) assessments of fatigue, depressive symptoms and proposed mediators, during two 2-week periods in the study (initial: 0-2 weeks, later: 8-10 weeks). Summaries of the proportion and frequency of missing daily assessments will inform the feasibility of collecting this type of data. Graphical displays of these daily reports will prove invaluable for informing both the patterns of the respective symptoms and mechanisms in and of themselves, and also for informing the optimal representation of the patterns in analyses with the recalled measures. Depending on missing data, study group differences in daily (or mean 2-day) values will be evaluated using mixed-effects generalized linear modeling. Findings and effect sizes garnered from these analyses will be compared to those resulting from recalled measures. Informed by the graphical displays, several summary indices of each of the two daily assessment periods (peak value, mean, coefficient of variation) will be generated for use in multi-method, multi-trait analyses of similarities and differences in the patterns of associations among the daily and recalled measures. This analysis will further inform which measures (and/or which summary indices) appear to be the best and most sensitive indices to use in future studies.

**Specific Aim 3:** Open-ended and interview data will be coded by the Qualitative Research Core led by [name] (Collaborator). [name] will consult with the Core to develop a coding system and also code 10% of the responses to assess reliability. Coded responses will be interpreted with a thematic analysis. The number of participants interviewed (20-40) will be decided by when thematic saturation is reached. Qualitative information gained will enrich quantitative results and inform the protocol of a larger trial.

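### Aim 2 compares daily with recalled effect sizes to inform which measure is most sensitive, but plans no uncertainty for that paired comparison, and its peak index falls on average as daily surveys are missed

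*Combined protocol and SAP*

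**What the plan says.** Under Specific Aim 2, section 9.6 sets out two steps.

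1. Arm differences in daily (or two-day mean) values are estimated by mixed-effects models. Then: "Findings and effect sizes garnered from these analyses will be compared to those resulting from recalled measures".
2. For the two-week periods at weeks 0-2 and 8-10, "several summary indices of each of the two daily assessment periods (peak value, mean, coefficient of variation) will be generated". These indices enter a multi-method, multi-trait analysis of associations among daily and recalled measures. That analysis is to help show "which measures (and/or which summary indices) appear to be the best and most sensitive indices to use in future studies".

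The section does not define sensitivity and gives no interval for the difference between two effect sizes. It sets no minimum number of completed days for an index. It does plan to summarise missing daily assessments. Elsewhere in 9.6, bootstrap 95% intervals are planned for individual estimates (in the Aim 1 text), and imputation is ruled out for missed assessments and drop-out.

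Section 2.1 explains why the peak matters: "symptoms peak approximately 3-5 days following treatment and then improve".

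**The concern.** A stated product of Aim 2 is guidance on which measure to carry into later studies. Two features weaken it.

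First, a daily and a recalled effect size from the same small sample can differ by chance. Without an interval for the difference, a reader cannot tell a more sensitive measure from a luckier one. Two separate intervals do not answer this, because the estimates are correlated.

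Second, the observed peak depends on how many days were completed, and on which ones. If completion differs between people or between the two periods, part of the variation in the peak reflects survey completion rather than symptoms. That distorts its associations with the recalled measures and its comparison between weeks 0-2 and weeks 8-10.

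**Working it through.** **The plan's own precision figure.** Section 9.2 gives 80% confidence that the estimated SD is no more than 10% below the true SD with N = 44, or no more than 14% below if the SD differs by group. Using P(s ≥ fσ) = P(χ² with df degrees of freedom ≥ f²·df):

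- N = 44, df = 43, f = 0.90: 0.808.
- 22 per arm, df = 21, f = 0.86: 0.795.

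Both agree with the stated 0.80. This is the plan's only precision figure; none is given for Aim 2.

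**Inputs for Aim 2.** The précis states: "The target population is 44 participants, 22 in each group". Section 9.2 anticipates about 15% dropout, so 44 × 0.85 = 37.4 remain, taken as 18 and 19. The documents give neither the correlation between measures (ρ) nor the true gap between their effects. I assume ρ = 0.5-0.9 and gaps of 0.1-0.3, and treat each measure as one summary per person.

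**Ordering two measures.**

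- SE(d) = √(1/18 + 1/19) = 0.33, a 95% half-width of about 0.65. On the recalled fatigue scale, with the SD of 8 from section 9.2, that standard error is 0.329 × 8 = 2.6 T-score points.
- SE of the difference = SE(d) × √(2(1 − ρ)).
- P(correct order) = Φ(gap / SE of the difference).

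| ρ | SE of difference | 95% half-width | Gap 0.1 | Gap 0.2 | Gap 0.3 |
|---|---|---|---|---|---|
| 0.5 | 0.33 | 0.64 | 62% | 73% | 82% |
| 0.7 | 0.26 | 0.50 | 65% | 78% | 88% |
| 0.8 | 0.21 | 0.41 | 69% | 83% | 93% |
| 0.9 | 0.15 | 0.29 | 75% | 91% | 98% |

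A coin toss would score 50%.

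**The peak under missed days.** I simulated 14 daily values per person, with intraclass correlation 0.5 or 0.7, with and without a rise on days 3-5, and with day-to-day autocorrelation 0 or 0.4. All of these settings are assumptions. The average fall in the observed peak, in SDs of the peak, was:

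| Days missed | At random | Worse days missed more (log-odds 0.7 per SD, assumed) |
|---|---|---|
| 10% | 0.03-0.05 | 0.06-0.11 |
| 20% | 0.06-0.10 | 0.11-0.23 |
| 30% | 0.10-0.17 | 0.18-0.34 |
| 50% | 0.21-0.35 | 0.34-0.62 |

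- The two-week mean does not shift when days are missed at random. It shifts less than the peak when worse days are skipped: with intraclass correlation 0.7, the day 3-5 rise, no autocorrelation and 30% missed, the peak falls by 0.206 and the mean by 0.069, in score units.
- These are averages. One person's peak falls only if the peak day itself is missed, which at 20% random missingness is about 20% of people.
- Scores were simulated as continuous. Ties on the short daily scale would make the falls smaller.

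**The case against.** The best reply is that the plan describes no contest between arm effects. The indices feed an association analysis, arm effect sizes are compared only for daily against recalled measures, and the wording is to inform, not to select. This stands. A reader might infer that the plan picks a winner among peak, mean and coefficient of variation by their observed arm effects, and so carries an inflated effect forward. The documents do not support that: no arm effect per index is planned, and section 9.2 bases the next trial's power on a clinically meaningful difference and the estimated SD.

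A reader might also infer that the peak creates a false difference between arms. Arm differences are to be tested on daily or two-day values, not on the peak. An arm comparison of peaks would be biased only if missingness differed by arm or with severity. Equal random missingness leaves it at zero.

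Safeguards also exist. Missing daily assessments are summarised, completion is tracked, and staff call participants who miss the first two surveys (section 6.2). These show the extent of missing data but do not correct the index. The single-estimate bootstrap intervals do not cover the paired difference.

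Finally, this is an exploratory part of a secondary aim in a pilot, and a wrong choice between near-equal measures costs little. That bears on severity and is accepted.

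**Conclusion.** The point holds as a minor one. With about 37 completers, the daily and recalled measures cannot be reliably ordered if their true standardised effects differ by about 0.1 (62-75% correct), while a gap of 0.3 is usually ordered correctly (82-98%). To call the whole exercise chance would therefore go too far; that describes only near-equal measures. The plan gives no interval from which a reader could tell which case applies.

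The observed peak falls on average with missed days, by about 0.10-0.17 SD at 30% missing at random and by more if worse days are skipped. The size rests on the assumed correlations, gaps, daily variance structure and missingness, none of which the documents supply.

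**What to change.** Before analysis, add the following to section 9.6:

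- Report the daily-minus-recalled difference in standardised effect with a 95% bootstrap interval that resamples participants and keeps each person's measures together. Call one measure more sensitive only if the interval excludes zero.
- Otherwise state that the measures cannot be ranked, and describe completion, reliability and within-person response to infusion pooled over arms. None of these depends on a yoga effect.
- Replace the raw maximum with a model-predicted peak or the mean over days 3-5 after infusion, or report one of these beside it. They are less biased, not unbiased, if worse days are skipped. Some participants may have no day 3-5 value: at 50% random missingness, 0.5³ = 12.5% would have none.
- Report daily completion by arm and by period.
- Label the ranking exploratory.

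The cost is a few lines of SAP text and a little programming, with no new data. The drawback is that the measures may well prove impossible to rank: at the half-widths above, the observed difference would need to exceed roughly 0.29 to 0.64.

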## 10. DATA COLLECTION AND QUALITY ASSURANCE

### 10.1 Data Collection Forms

Questionnaires and blood draws will be collected by a blinded STM. Data records for each participant will be identified by a unique study code number that does not contain personal identifying information. Data collection forms which only have ID

numbers will be stored in a locking cabinet at CCC-WFU or in the PI's office building while on study at Wake Forest University. Data from these documents, clinical data from the medical chart and data collected via daily automated surveys will be entered into a REDCap database at Wake Forest University. The actigraphy data, audio recorded semi-structured interviews and videos of the intervention sessions will also only be coded by study ID number. Data collection forms are presented in the appendices as outlined in the Table of Contents.

All participants will be assigned a study ID number; however, it is necessary for the study team to know participants names during time on-study. Names will be maintained in a participant tracking database accessible only to approved study staff through password protected files stored on a secure server, not on laptops or thumb drives. To protect confidentiality, all data will be stored in a locked file cabinet located in the secured office of a STM or PI. All computers and data files will be password protected. All data processed will be in aggregate form and data collection forms will only be labeled with participant's unique identification number.

## **10.2 Data Management**

The clinical site will not be responsible for data collection or management. Some data will be extracted from the medical record at the clinical site, though this data is part of routine monitoring and care of the patients.

CCC-WFU will serve as the data coordinating center. Data from Vanderbilt-Ingram Cancer center will be transferred securely to CCC-WFU utilizing Accelion.

Data collection forms are outlined in section 9.5 Outcomes and stored as summarized in the following table.

### **Summary of Data Storage**

Informed consent document	Electronic Medical Record
Protocol registration form	ORIS
Study questionnaires (Weeks 0, 10, 14)	REDCap
Daily survey data	REDCap
Treatment fidelity data	REDCap
Clinical data	REDCap
Actigraphy data	Excel Files on Secure Server
Inflammation data	Excel Files on Secure Server
Adherence data	Excel Files on Secure Server
Qualitative data	Box hosted through Vanderbilt University and on Secure Server
Adverse events	ORIS

## **10.3 Quality Assurance**

### **10.3.1 Training**

All research staff will have completed the online Collaborative Institutional Training Initiative Training (CITI) prior to participation in research activities. [name] will

directly oversee training of research staff in regards to conducting the planned research.

### **10.3.2 Quality Control Committee**

The study team will generate Study Reports for the IMC and will provide information on the following study parameters: recruitment of subjects to the pilot study, adherence to the interventions, and adverse events that may be related to the interventions.

The frequency of review for this study differs according to the type of data and can be summarized in the following Table.

#### **Frequency of data review**

Data type	Frequency of review	Reviewer
Subject accrual (including compliance with protocol enrollment criteria)	Quarterly	PI, Independent Monitor(s)
Status of all enrolled subjects, as of date of reporting	Quarterly	PI, Independent Monitor(s)
Adherence data regarding study visits and intervention	Quarterly	PI, Independent Monitor(s)
AEs and rates	Quarterly	PI, Independent Monitor(s)
SAEs	Per occurrence	PI, Independent Monitor(s), IRB, NCCIH

### **10.3.3 Metrics**

Review of the rate of subject accrual and compliance with inclusion/exclusion criteria will occur monthly by the PI during the first three months and then every quarter (4 months) to ensure that a sufficient number of participants are being enrolled and that they meet eligibility criteria and the targeted ethnic diversity goals outlined in the grant proposal (Targeted/Planned Enrollment Table).

Adherence of participants will be evaluated by documentation of participation in interventions during chemotherapy. We will consider high adherence to the intervention if subjects participate in 80% of the in-person interventions. If on review, adherence is below this threshold, [name] will convene a conference call to discuss methods for improving adherence.

[name] or study staff will also review all data collection forms on an ongoing basis (i.e., quarterly) for data completeness and accuracy as well as protocol compliance. A

study member not involved in data collection will enter the data. At least ten percent of all data entered from questionnaires will be randomly selected and verified for accuracy against original source documents. Any discrepancies will be discussed with the Independent Monitors. Data will also be reviewed for outliers and to determine if values are missing at random prior to analysis. [name] will provide quarterly updates to the IMC and research mentors regarding patient accrual.

#### **10.3.4 Protocol Deviations**

Protocol deviations will be captured through direct observation by research staff regarding patient recruitment and enrollment, intervention administration, adherence, and safety monitoring. Protocol deviations will be reviewed by the principal investigator and discussed with research mentors and as needed with the IMC.

#### **10.3.5 Monitoring**

[name] will monitor for protocol compliance, data quality, and review of documentation to assure protocol compliance. This will include review of informed consent process (upon enrollment), adverse event reporting (upon occurrence), and data collection (monthly).

### **11. PARTICIPANT RIGHTS AND CONFIDENTIALITY**

#### **11.1 Institutional Review Board (IRB) Review**

This protocol and the informed consent document and any subsequent modifications will be reviewed and approved by the IRB or ethics committee responsible for oversight of the study.

#### **11.2 Informed Consent Forms**

Written informed consent will be obtained from each subject at entry into the study. Informed consent is obtained by the following process:

1. The patient will be asked to review the study consent form.
2. The PI or STM will meet with the patient either in person or by telephone to review the form, to confirm the patient understands the study, and to answer any questions that the patient might have.
3. Once the patient demonstrates understanding of the study and agrees to participate in the study, the consent will be signed remotely or in person. If signed remotely, patients will be asked to send the form back to us by a secure means, as well as bring the original with them to their next clinic visit.

A copy of the consent form will be given to the participant the next time they are in clinic, and the original copy will be kept in the participant's file. Patients who cannot consent for themselves in English will not be eligible to participate.

### **11.3 Participant Confidentiality**

Any data, specimens, forms, reports, video recordings, and other records that leave the site will be identified only by a participant identification number (Participant ID, PID) to maintain confidentiality. All records will be kept in a locked file cabinet. All computer entry and networking programs will be done using PIDs only. Information will not be released without written permission of the participant, except as necessary for monitoring by the IRB and the NCCIH.

### **11.4 Study Discontinuation**

The study may be discontinued at any time by the IRB, the NCCIH, or other government agencies as part of their duties to ensure that research participants are protected.

## **12. COMMITTEES**

The Independent Monitoring Committee (IMC) for this study is comprised of members of the Wake Forest School of Medicine's Institutional Data and Safety Monitoring Board who are not associated with this research project and thus work independently of the PI, [name]. They are not part of the key personnel involved in this grant. They are qualified to review the patient safety data generated by this study because of their respective unique expertise in the areas of oncology, mental health/ethics and statistics.

## **13. PUBLICATION OF RESEARCH FINDINGS**

Any presentation, abstract, or manuscript will be made available for review by the sponsor and the NCCIH prior to submission.

## 15. SUPPLEMENTS/APPENDICES

### 15.2.1 Appendix A: Informed Consent Documents and Form for Documentation

### 15.2.2 Appendix B: Yoga Skills Training Home Practice Guide

### 15.2.3 Appendix C: Yoga Skills Training Home Diary

### 15.2.4 Appendix D: Attention Control Home Diary

### 15.2.5 Appendix E: Treatment Fidelity Forms

